9.3 Suspected Unexpected Serious Adverse Reaction, SUSAR

The sponsor reports all SUSARs that arise during the trial to The Medicinal Product Agency and Uppsala's Ethics committee. Reports will be done by sending the CIOMS form to the MPA since sponsor does not have the resources to report electronically to the EudraVigilance database.

A SUSAR that results in death or is life-threatening must be reported promptly and no later than 7 days after it occurred and was known by sponsor. Relevant follow-up information should be sent within another 8 days. Any other SUSARs should be reported as soon as possible but not later than 15 days after being brought to sponsors attention.

10 STATISTICS

10.1 Determination of Clinical response

There is no power calculation due to the nature of this study, a pilot study. If at least 2 patients improve significantly we aim to continue with a controlled study.

Primary outcome

Reduction in PANSS score (30 items) is the primary outcome. 40% reduction in PANSS is regarded as a treatment response.

Secondary outcomes

CGI-I score 1 or 2 which corresponds to much or very much improved at week 20 is regarded as response. Assuming a SD of 1 in our sample we will be able to detect differences between the means before and after treatment corresponding to 0.64 points on the CGI-I scale.

Changes in PSP and clinician rated CGI-S score between enrollment and week 20.

PSP gives a score between 0-100 for disability.

CGI-S is a clinician rated measure of overall clinical severity that is rated on a scale between 1 and 7. This measure also has a floor effect that affects healthy participants, for a person with no clinical complaints or problems (which is most people in a population) will get a score of 1. This floor effect is not relevant to our study population. The score 7, which indicates the highest level of severity is phrased as "Among the most extremely ill patients". This may be true to the patient group in the present study. However, since patients currently in need of compulsory care are excluded from the study, a ceiling effect of the measure is unlikely.

Repeated measures of the PSP and CGI-S will be analysed using a repeated measures ANOVA.

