- 8) if antipsychotic treatment is prescribed the plasma concentrations of the drug must be tested and shown to be within therapeutic interval.
- 9) subjects should be judged by the investigator to be lucid and oriented to person, place, time, and situation when giving the informed consent.
- 10) immunoglobulin levels within the normal range

EXCLUSION CRITERIA

- 1) on-going immunomodulatory treatment
- 2) pregnancy or breast-feeding
- 3) weight below 40 kg
- 4) clinically relevant on-going infection
- 5) chronic infections
- 6) positive screening test for hepatitis B, C, HIV or tuberculosis
- 7) any change of psychotropic medication within the previous 4 weeks
- 8) "much" or "very much improved" already at baseline according to CGI-I i.e. scores of 1 or 2 by the clinician
- 9) severe heart failure (NYHA grade IV) or other severe heart disease or history of cardiac

arrhythmia or myocardial infarction

- 10) unable to make an informed decision to consent to the trial
- 11) in compulsory treatment
- 12) treatment with clozapine within the last 2 months
- 13) previous treatments with immunosuppressive agents
- 14) malignancy currently or within 2 years prior to inclusion

STUDY DESIGN

Open pilot study, in addition a qualitative study using content analysis approach.

Participants will be treated initially for 20 weeks and followed for 52 weeks.

STATISTICAL ANALYSIS

Determination of Sample Size

In this pilot study population of 12 participants is presumed to be large enough to determine any effect of rituximab.

Primary objective: Effect of rituximab on schizophrenia symptoms measured with PANSS

The primary outcome (as described in section 5.2) is difference between baseline and endpoint on PANSS scale. 40% reduction in the PANSS scale.

Analyses of laboratory data related to clinical response

Laboratory data will consist of: plasma protein concentrations and leukocyte mRNA expression values for a number of cytokines and related substances (inflammatory markers); total number of B-lymphocytes and number of cells from various B-cell subsets at week 5, 12 and 20, as measured through highly sensitive flow cytometry (HSFC); plasma proteins and lipids as measured through metabolomics analysis; and blood levels of markers for gut permeability.

In order to examine whether baseline characteristics can predict treatment response, baseline values of all these measurements will

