- Difference from baseline up to week 40 in inflammatory markers in blood (gene expression and proteins) in relationship to clinical response
- Change in PSP, clinician administered version, measuring overall disability from baseline up to week 40
- Change from baseline up to week 40 of illness severity (CGI-S) assessed by the clinician
- Proportion of responders to treatment, i.e. rated as "Much improved" or "Very much improved" since baseline according to CGI-I
- Life quality measured with BBQ

Other outcome measures are:

- B-cell subpopulations at week 40 in relation to clinical response
- Changes in cognitive functioning at 40 weeks:

- Neuropsychological functioning assessed with e.g. visuospatial and executive tests
- Change from baseline on rating scales that measure psychiatric symptoms specific for each diagnosis (shown below) *during the past 2 weeks*
 - BOCS for measuring obsessive-compulsive symptoms
 - RAADS-R for measuring autistic symptoms
 - PANSS for measuring psychotic symptoms
 - BFCR to measure catatonic symptoms
 - HADS for measuring depressive and anxiety symptoms

Follow-up, 1 year after treatment start. Outcome is PANSS and CGI-I in relation to treatment and evaluated by the treating clinician, the patient's self-assessment and a next of kin.

Qualitative content analysis

At endpoint 1, after 20 weeks, a qualitative content analysis will be performed.

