Participants with severe SSD may not be able to respond to all questions or fill out rating scales. However, we will then obtain independent information whether the patient is improved or not according to CGI-I and PANSS even though h/she may not be able to fill out rating scales. Thus our primary outcome measure can be used at all times regardless of the state of the patient.

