6.3 Withdrawal of patients

The patients can at any time choose to stop participating in the study without giving any reason for this. If possible, the reason for the patient leaving the study should be recorded. Data collected up to the subject's leaving the study will be used in the analysis of the study.

The investigator can remove a patient from the study due to safety reasons or in case the patient is not able to comply with the protocol.

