10.2 Statistical methods and analytical plan

10.2.1 Primary objective: Improvement reflected in change in PANSS score

To investigate whether markedly ill, treatment-resistant, psychiatric patients according to our inclusion/exclusion criteria are significantly improved after treatment with the immunomodulatory drug rituximab (as addition to the patients' standard treatment).

We will analyse the clinical data on a modified intention-to-treat (ITT) definition basis, i.e. including treatment dropouts who received at least one dose of rituximab as well as completers. In addition, a completer-only analysis will be performed. *The primary outcome* is change in PANSS score, assessed by a clinician.

Secondary outcomes: CGI-I score (range 1-7). All CGI-I ratings are performed by three independent raters (the patient, his or her next of kin and a clinician). The mean value of these three values will be used as the patients' scores. If one of the values is missing, the mean will be calculated using only two values.

One secondary outcome is binary: the proportion of responders to treatment at week 20 (and similarly at week 40). Treatment response is defined as a mean value below 2.5 on the CGI-I (calculated as above), which corresponds to the scale step descriptors "much improved" or "very much improved". Non-response is defined as a mean CGI-I value of 2.5 or higher.

The continuous secondary outcome variables at the 20-week and 40-week end points (CGI-S, PSP, and diagnosis specific rating scales) will be included in analysis of covariance (ANCOVA) models, controlling for baseline measures and demographic variables.

Side-effects will be closely monitored and types, frequency, severity and seriousness will be reported.

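### Does the go sentence in 10.1 need rewriting because it does not define improvement, does not say how early leavers count, and sits beside an optimistic synopsis line on n = 12?

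*Combined protocol and SAP*

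**What the plan says.** Section 10.1 says that no power calculation was done because this is a pilot, and then gives the progression aim: "If at least 2 patients improve significantly we aim to continue with a controlled study". The next paragraph, on the primary outcome, adds "40% reduction in PANSS is regarded as a treatment response", with no week. The paragraph on secondary outcomes adds "CGI-I score 1 or 2 which corresponds to much or very much improved at week 20 is regarded as response".

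On timing, 5.2 ties the first endpoint to week 20 ("At endpoint 1, after 20 weeks, a qualitative content analysis will be performed"), as does 7.1. The Synopsis, under long-term outcomes, describes the week-40 primary outcome as a repeat of the week-20 one and names PANSS. Table 1 schedules PANSS at weeks 0, 12, 20, 40 and 52.

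On patients who leave, 6.3 says "Data collected up to the subject's leaving the study will be used in the analysis of the study". Section 10.2.1 uses a modified ITT set, "including treatment dropouts who received at least one dose of rituximab as well as completers", plus a completer analysis. Section 6.1 covers patients too ill to complete scales: "Thus our primary outcome measure can be used at all times regardless of the state of the patient".

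On size, the Synopsis states that a population of "12 participants is presumed to be large enough to determine any effect of rituximab". Section 12.4 says instead that so small a group could hide an effect.

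**The concern.** For a single patient, improving significantly has no statistical meaning, so a reader looks for a definition and finds two kinds of response in the same section. Only the secondary one, on CGI-I, carries a week. With a threshold of two, the status of one or two patients can settle the count. A patient who had a 40% PANSS fall at week 12 and then left could be counted either way, and that choice could be made after the results are known.

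The synopsis sentence adds to the worry. Read literally, it suggests that a disappointing count would be informative about absence of effect, which 12 patients cannot support. At stake is the only stated criterion for moving to a controlled study.

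**Working it through.** **The plan's own figure.** Section 10.1 gives a detectable mean difference of 0.64 on CGI-I with SD 1. Taking n = 12 and assuming a two-sided 5% level, t(0.975, 11 df) × SD/√n = 2.201 × 1/3.464 = 0.635, which rounds to 0.64. It is therefore the smallest observed mean that would reach significance. Power at a true difference of 0.64 SD is about 52%, and 80% power at n = 12 needs about 0.89 SD. So the synopsis line is too strong for a mean-change analysis as well.

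**What the go sentence means.** Read side by side:
- PANSS is the primary outcome in the Synopsis, 5.2, 10.1 and 10.2.1. CGI-I response is labelled secondary in each of these places.
- The 40% cut-off stands in the paragraph after the go sentence, and again under the primary objective in the Synopsis.
- Week 20 is endpoint 1, and the week-40 primary outcome is described as the same measure taken later.
- Treatment is a single infusion (7.1, 8.2), so every treated patient meets the one-dose condition in 10.2.1. Only follow-up can be lost.

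These lead to one reading: at least 2 treated patients with a PANSS reduction of 40% or more at week 20.

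**How the rule behaves on that reading.** The documents give no response rates, so p is an assumed range. P(at least 2 of n) = 1 − (1−p)^n − n·p·(1−p)^(n−1). For n = 12 and p = 0.10 this is 1 − 0.282 − 0.377 = 0.341.

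| True rate p | P(≥2 of 12) | P(<2 of 12) |
|---|---|---|
| 5% | 11.8% | 88.2% |
| 10% | 34.1% | 65.9% |
| 15% | 55.7% | 44.3% |
| 20% | 72.5% | 27.5% |

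Solving for 80% gives p of about 23%. Exact 95% intervals are 0/12: 0 to 26.5% (upper limit 1 − 0.025^(1/12)); 1/12: 0.2% to 38.5%; 2/12: 2.1% to 48.4%. These agree with 12.4. They describe the count, not the mean PANSS change that follows the sample-size line in the Synopsis.

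**Early leavers.** Assume that 1 to 3 patients leave after week 12, that leaving is unrelated to response, and that week-12 and week-20 response rates are equal. Counting leavers by their week-12 PANSS keeps n = 12; counting them as non-responders leaves 11, 10 or 9 who can respond.

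| Leavers | p = 10%: week-12 value / non-response | p = 20%: week-12 value / non-response |
|---|---|---|
| 1 | 34.1% / 30.3% | 72.5% / 67.8% |
| 2 | 34.1% / 26.4% | 72.5% / 62.4% |
| 3 | 34.1% / 22.5% | 72.5% / 56.4% |

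With two leavers the convention moves the chance of reaching two by 34.1 − 26.4 = 7.7 points at p = 10%, and by 72.5 − 62.4 = 10.1 points at p = 20%.

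**The case for a change.** The best case for a change is that it is cheap. If the meaning is obvious, one sentence records it. Even on the obvious reading the status of a leaver stays open and could be settled after the data are seen. A mistaken go would be tested by the controlled study, but a mistaken stop would have no such correction. The Synopsis and 12.4 are both current text and do not agree.

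Some of this stands. The link is unwritten, the leaver convention is unwritten, and the two statements on size pull apart.

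The rest is weaker. The go sentence runs in one direction and states an aim; nothing says that a count of 0 or 1 ends development or is to be read as no effect, so a formal no-go and its miss rate are inferences. The PANSS analysis and the later PANSS assessments go ahead whatever the count. The usual remedy, counting leavers as non-responders, makes reaching two less likely, which adds to the very error said to have no correction. It also sets aside a week-12 rating although 6.3 says data up to leaving are used. It is one fair convention among several.

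**Conclusion.** No change is needed. The missing link is a gap that any analyst would close in the same way from the surrounding text. How a leaver counts is a trade-off between two defensible conventions. On the assumptions above, the choice shifts the chance of reaching two responders by 3.8 to 11.6 points at a 10% response rate and by 4.7 to 16.1 points at 20%. With 12 patients, a report can list each patient's PANSS course and show the count both ways, with an exact interval.

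The synopsis line is loose and the arithmetic does not support it. It carries no power or detectable effect, 10.1 disclaims a power calculation, and 12.4 states the limitation openly. Rewording it would change nothing that the trial does or concludes.

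This rests on reading the rule as a 40% PANSS reduction at week 20, on response rates and leaver numbers that are assumed because the documents give none, and on the go sentence remaining a non-binding aim.

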5.2 Outcomes

Primary outcome

The primary outcome measure is change in symptoms measured as change in PANSS score.

Secondary outcome

- Global improvement at week 20, according to a balanced assessment (mean value of three independent assessors: 1) The treating clinician, 2) The patient's self-assessment and 3) A next-of-kin) using the Clinical Global Impression-Improvement (CGI-I) scale (range 1-7; 1 representing "Very much improved").
- Change in Personal and Social Performance Scale (PCP) measuring overall disability
- Change from baseline up to week 20 of illness severity (CGI-S) assessed by the clinician
- Difference from baseline up to week 20 in inflammatory markers in blood (gene expression and proteins) in relationship to clinical response (CGI-I)
- Proportion of responders to treatment, i.e. rated as much or very much improved since baseline according to CGI-I assessed by three different informants: 1) The treating clinician, 2) The patient's self-assessment and 3) A next of kin. If the mean value of these three is below 2.5 then the patient will be regarded as a responder (representing much or very much improved since baseline).

- Safety and tolerability of rituximab during treatment for SSD measured with the questionnaire Any Adverse Reactions (AAR).

Other outcome measures

- B-cell depletion at week 5, and B-cell subpopulations at week 20 in relation to clinical response and baseline levels of B-cells
- Changes in cognitive functioning at 20 weeks:
 - Neuropsychological functioning assessed with e.g. visuospatial and executive tests
- Change from baseline on rating scales that measure psychiatric symptoms specific for each diagnosis (shown below) *during the past 2 weeks*
 - BOCS for measuring obsessive-compulsive symptoms
 - RAADS-R for measuring autistic symptoms
 - PANSS for measuring psychotic symptoms
 - BFCR to measure catatonic symptoms
 - HADS for measuring depressive and anxiety symptoms

Long-term outcomes

40 weeks follow-up:

Outcome measures for long term are identical to that used at 20 week.

Change in symptoms measured as change in PANSS score.

The secondary outcome measures are:

- Global improvement at week 20, according to a balanced assessment (mean value of three independent assessors: 1) The treating clinician, 2) The patient's self-assessment and 3) A next-of-kin) using the Clinical Global Impression-Improvement (CGI-I) scale (range 1-7; 1 representing "Very much improved").

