7.1.2. Rating scales and tests

If more than one clinician will assess the patients rating calibration training for obtaining agreement on scorings will be performed.

Due to the large data collection in combination with the severity of the disorder in these patients missing data will be unavoidable. We will try to avoid missing data by providing clarification if a patient cannot understand the meaning of a question. For each symptom rating scale the response rate is set at a minimum of 80 % of the questions. Isolated missing scores will be replaced with the individual mean.

Demographics

- Background data collection form
- Pans Data Collection Form provides information about inherited physical and psychiatric disorders within the family.

Diagnostic interviews

- Mini International Neuropsychiatric Interview (M.I.N.I. version 7) is a structured clinical interview for psychiatric disorders. In addition the childhood onset diagnoses from the M.I.N.I. kid version will be amended to the adult version of M.I.N.I. (66, 67)
- PsychoNeuroinflammatory Related Signs and Symptoms Inventory (PNISSI) in order to identify and measure symptoms related to neuro-inflammation and diagnose PANDAS and PANS (68)

Assessment of severity, improvement and quality of life

- Clinical Global Impression-Improvement scale (CGI-I) measures change of symptoms on a 7 point Likert scale. CGI-I will also be administered to the next-of-kin (69)
- Patient's Global Evaluation (PGE) provides a self-administered global measure of improvement on a 7 point Likert scale (70)
- Clinical Global Impression-Severity scale (CGI-S) provides a global measure of illness severity on a 7 point Likert scale (69)
- Global Assessment of Functioning (GAF) measures general disability and symptom burden (71)
- Personal and Social Performance Scale (PSP) (72). The PSP is a 100-point single-item rating scale, subdivided into 10 equal intervals. The ratings are based mainly on the assessment of patient's functioning in four main areas: 1) socially useful activities; 2) personal and social relationships; 3) self-care; and 4) disturbing and aggressive behaviours.
- Level 1 Cross-cutting symptom measure of global symptom severity is a patient or informant rated measure included in the DSM-5, which assesses mental health domains that are important across psychiatric diagnoses. It includes 13 domains. We will use it with the clinician's assistance for adults (73)

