7.1.4.8 Qualitative content analysis

The 12 participants from the study will be interviewed about their experiences about participating in the study, using a semi structured interview guide. The questions will be focusing on the participants' experiences about the treatment, the approach from the staff their feelings about their psychiatric diagnosis. Our hypothesis is that the patients may have other thought about their psychiatric condition as it now can be viewed as an inflammatory disorder instead of purely a mental condition. Also we are interested in if the participants have reflected on any change in the approach of the staff since they now are regarded as “somatically ill patients” not simply “psychiatric patients”. The interviews will be transcribed verbatim and analyzed with qualitative content analysis.

Table 1 Study plan

Week		
-4 – 0	Screening prior to treatment with rituximab Decision on inclusion / exclusion	
 • Evaluation of suitability • Vaccination check up (+varicella) • Information to not use attenuated vaccines, what risks are involved and signs of immunosuppression • Consent form • Information card about drug study participation • Demographics questionnaire including FTF-Brief • Treatment history • PNISSI and fine motor examination • Physical examination • Check anti-hypertensive medication* • Test for group A streptococcus • Blood sample • Routine safety: Test of hepatitis, HIV, TB and routine tests • Therapeutic drug monitoring • Urine: illicit drug screen and pregnancy test, inflammatory markers • Assessments (CGI-S and MINI, psychiatric rating scales, GAF, EQ-5D, Level 1 Cross-cutting symptom measure of global symptom severity) • Functioning: PSP and BBQ • Side-effects, AAR • UKU • Client satisfaction questionnaire (CSQ) • Cognitive tests Video recording I • Lumbar puncture (optional) • Faeces biopsy and sample (optional) • fMRI (optional)
0	Baseline Rituximab dose 1000 mg	
 • Assessments (PANSS, CGI-I**, PGE, CGI-S) • Blood sample (inflammatory markers)
2	Nurse check-up	
 • Side-effects, AAR
5, (+/- 1 week)		
 • Side-effects, AAR • Patient evaluated improvement (PGE) • Blood sample (B-cell population)
8	Nurse check-up	
 • Side-effects, AAR • Patient evaluated improvement (PGE)

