12		
 • Assessments (PANSS, CGI-I**, PGE, CGI-S) • Side-effects, AAR • Patient evaluated improvement (PGE) • Blood sample (B-cell population) • Video recording II
16 (+/- 1 week)	Nurse check-up	
 • Side-effects, AAR • Patient evaluated improvement (PGE)
20-23	20 w	
Interview + Assessments (PANSS, CGI-I*, PGE, CGI-S, and MINI, psychiatric rating scales, GAF, EQ-5D, Level 1 Cross-cutting symptom measure of global symptom severity)
 
 • PSP • Side-effects, AAR

		
• UKU• Client satisfaction questionnaire (CSQ)• Physical examination• Cognitive and motor tests (from PNISSI and Nine-Hole Peg Test)• Video recording III• Blood sample• Lumbar puncture (optional)• Faeces sample (optional)• Urine sample• fMRI (optional)
20-24	Clinician	
• Extended interview for content analysis
24 (+/- 1 week)	Nurse check-up	
• Patient evaluated improvement (PGE)• Side-effects, AAR
32 (+/- 1 week)	Nurse check-up	
• Patient evaluated improvement (PGE)• Side-effects, AAR
40-43	40 w	
• Interview + Assessments (PANSS; CGI-I*, PGE, CGI-S, and MINI, psychiatric rating scales, GAF, EQ-5D)• PSP and BBQ• Client satisfaction questionnaire (CSQ)• Side-effects, AAR, UKU• Blood sample• Cognitive tests• Video recording IV
52 (+/- 1 week)	1 year follow-up	
• Assessments (PANSS, CGI-I, PGE, CGI-S, GAF)• Side-effects, AAR

*if the patient is treated with antihypertensive medication these should be withdrawn 12 h prior to the rituximab treatment

**evaluated by clinician and next-of-kin

Table 2

Week			-4 - 0	0	1	2	5	8	12	16	20	24	32	40	52
Visit			1	2	3	4 (nur se)	5	6 (nur se)	7	8 (nur se)	9	10 (nurse /other)	11 (nur se)	12	13
Activity/ Assessment number	CRF Y/N	Time to complete		Pre-Study Screening	Baseline 1:0						20w			40w	
ENROLMENT Eligibility screen, Consent form, Demographics questionnaire, Treatment history, PNISSI, Physical examination, FTF-Brief. Routine blood tests, hepatitis, HIV, TB. Vaccination check up (+varicella). Therapeutic drug monitoring, U-illicit drug screening,		60 min	x												
Pregnancy test (females)			x												
INTERVENTION Rituximab, Dose 1: 4.5h				x:1											
ASSESSMENTS MINI, Psychiatric rating scales		45 min	x								x		x	x	x

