Level 1 Cross-cutting symptom measure of global symptom severity			x								x				
GAF, PSP		5 min	x							x		x		x	x
CSQ, BBQ, EQ-5D		10 min	x								x			x	
PANSS		20 min		x						x		x		x	x
CGI-S (clinician)		5 min	x	x						x		x		x	x

CGI-I (clinician and next of kin)		10 min		x				x		x			x	x
PGE (patient evaluated improvement)		5 min		x			x	x	x	x	x	x	x	x
UKU		10 min	x							x			x	
Side effect open check up questions and AAR		10 min	x			x	x	x	x	x	x	x	x	x
Blood sample		15 min	x	x		x		x		x			x	
Lumbar puncture		30 min	x							x				
Faeces sample		5 min	x							x				
Urine test (morning sample)		5 min	x							x				
fMRI		120 min	x							x				
Gut biopsy		30 min	x											
Cognitive and motor test		30 min	x							x				
Video recording		10 min	x					x		x			x	
Extended interview for content analysis		45 min								x				
Nurse in-between visits/ progress notes		10 min			x		x		x	x	x			

BBQ = Brunnsviken Brief Quality of Life Inventory; CGI-S = Clinical Global Impression-Severity scale; CGI-I = Clinical Global Impression-Improvement scale; CSQ = Client Satisfaction Questionnaire; GAF = Global Assessment of Function; MINI = Mini International Neuropsychiatric Interview; MRI = Magnetic Resonance Imaging; PGE = Patient's Global Evaluation of improvement; UKU = Udvælg Kliniske Undersøgelser, side effect rating scale; Personal and Social Performance (PSP) Scale; EuroQol Group EQ-5D; Any Adverse Reactions (AAR).

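### Does the 0.64-point detectable CGI-I difference, given without alpha, power or type of SD, need correcting?

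*Combined protocol and SAP*

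**What the plan says.** Section 10.1 begins with "There is no power calculation due to the nature of this study, a pilot study". Under its secondary outcomes it defines CGI-I response at week 20, assumes an SD of 1 in the sample, and states that "we will be able to detect differences between the means before and after treatment corresponding to 0.64 points on the CGI-I scale". Neither that section nor sections 10.2.1 to 10.2.4 or the synopsis give the alpha, sidedness, power, before/after correlation or type of SD behind the figure.

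The sample size is 12, single arm. The synopsis presents it as a presumption, not a calculated number: "In this pilot study population of 12 participants is presumed to be large enough to determine any effect of rituximab".

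On the scale itself, section 7.1.2 says "Clinical Global Impression-Improvement scale (CGI-I) measures change of symptoms on a 7 point Likert scale". Section 5.2 lists as a secondary outcome "Global improvement at week 20, according to a balanced assessment (mean value of three independent assessors", the raters being clinician, patient and next of kin. The schedule tables after section 7.1.4.8 place a CGI-I rating at week 0 and again at week 20. Table 2 labels the row "CGI-I (clinician and next of kin"), and the patient's own rating is collected separately as PGE.

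**The concern.** Saying that a study can detect a difference usually means that it has 80% or 90% power for it. The obvious inputs here (12 patients, SD 1, a two-sided 5% test) do not give 0.64 as a difference with 80% power; they give 0.89. What they do give as 0.64 is the smallest observed mean change that would reach significance, and a true effect of that size would be missed about half the time. If 0.64 is that threshold, the sentence promises more sensitivity than the design has, and a non-significant mean CGI-I change could be over-read as evidence of no effect.

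Two other features add to the unease. The section disclaims a power calculation and then makes a statement about detectability. And CGI-I is itself a rating of change, so a comparison of means before and after treatment needs a second look.

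**Working it through.** **Inputs from the documents.** n = 12 (synopsis); SD = 1 and difference = 0.64 (section 10.1).

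**Inputs not in the documents, assumed here.** Two-sided 5% test; one-sample t-test on within-patient changes, 11 degrees of freedom; SD 1 read first as the SD of the change.

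**Step 1: reproduce 0.64.** Half-width of the 95% confidence interval for the mean change:

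t(0.975, 11) × SD/√n = 2.201 × 1/√12 = 2.201 × 0.2887 = 0.635, which rounds to 0.64.

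So the figure is reproduced, as the smallest observed mean change that would be significant.

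**Step 2: power at a true change of 0.64.** Noncentrality = 0.64 × √12/1 = 2.217. The noncentral t with 11 degrees of freedom gives power 0.525. Under the same assumptions 80% power needs a true change of 0.889 and 90% needs 1.03. With a one-sided 5% test the power at 0.64 would be 0.667.

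**Step 3: read SD 1 as the SD at each visit.** With equal SDs and before/after correlation r, the SD of the change is √(2(1 − r)). Two-sided 5%:

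| r (assumed) | SD of change | Power at 0.64 | Difference with 80% power |
|---|---|---|---|
| 0 | 1.414 | 30% | 1.26 |
| 0.5 | 1.000 | 52% | 0.89 |
| 0.7 | 0.775 | 74% | 0.69 |
| 0.741 | 0.720 | 80% | 0.64 |
| 0.8 | 0.632 | 89% | 0.56 |

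Equal SDs are a further assumption. Exclusion criterion 8 removes patients whom the clinician already rates 1 or 2 on CGI-I at baseline, so the week-0 spread could be narrower. If the SDs were 0.5 at week 0 (assumed) and 1 at week 20, the SD of the change would be √(1.25 − r), and power at 0.64 would run from 44% (r = 0) to 85% (r = 0.8).

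**Step 4: other routes to 0.64.** A one-sided 10% test with SD of the change 1 has 80% power at 0.637. The row r = 0.741 above is another route; the 80%-power difference rounds to 0.64 for r between 0.737 and 0.745.

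At least three sets of inputs therefore return 0.64, one as a significance threshold and two as an 80%-power difference. The text does not choose between them.

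**Step 5: is the comparison defined?** The sentence itself names means before and after treatment, the sentence before it names week 20, and a week-0 CGI-I is scheduled. A before/after difference can be formed as described.

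**Step 6: what depends on 0.64?**

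- *Sample size:* no. Section 10.1 disclaims a power calculation and section 12.4 justifies the small group on ethical grounds.
- *Decision to proceed to a controlled study:* no. Section 10.1 ties it to at least 2 patients improving.
- *Primary outcome:* no. That is change in PANSS, with a 40% reduction counted as response.
- *A named test of mean CGI-I change at week 20:* none. The repeated-measures ANOVA in section 10.1 covers PSP and CGI-S. The ANCOVA in section 10.2.1 covers CGI-S, PSP and the diagnosis-specific scales. The t-tests and Mann-Whitney tests in section 10.2.3 cover PSP, CGI-S and the psychiatric rating scales. In section 10.2.1 CGI-I enters as a three-rater mean and as a responder proportion with a cut-off of 2.5.

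**The case for a change.** The strongest case for acting is that a protocol should not make a claim nobody can verify. On the simplest inputs the true power is 52%, not 80%, so the verb misleads. The repair would cost a sentence or two: label 0.64 as a half-width and add 0.89, give the real derivation, or delete the sentence. That the study is a pilot does not excuse it, since a section that disclaims power should not then promise detection.

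Much of this stands. The inputs are missing, and the wording is loose if 0.64 is the half-width. But overstatement is an inference from assumed inputs: the 30% to 89% range in Step 3 includes 80%. A reader who has just been told that there is no power calculation has little reason to take 0.64 as an 80%-power difference, and read as a significance threshold it is correct. The over-reading that is feared presupposes a test of mean CGI-I change that the week-20 analysis sections do not name. It is also countered by section 12.4, which says that the small sample may conceal an effect.

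The synopsis is more optimistic about 12 patients than section 12.4 is. That is a separate matter of wording and does not bear on 0.64.

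**Conclusion.** No change to the plan follows. What remains is an undocumented figure for a secondary outcome, not an arithmetic error. On the most direct reading (n = 12, SD of the change 1, two-sided 5% paired t-test) it is the confidence-interval half-width, with about 52% power at that value and 80% power at 0.89 points. All the power figures rest on an alpha, sidedness, test and type of SD that the documents do not state, and they move widely when those are varied.

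Relabelling or deleting the sentence would leave the sample size, the analyses and the rule for going on to a controlled study as they are. An analyst reporting mean CGI-I change would give the estimate with its confidence interval, and that interval shows the precision actually achieved, whatever the protocol projected.
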